7.1.4.2 Peripheral Blood Mononuclear Cell (PBMC) Collection

In all patients, approximately 60 mL of whole blood will be collected into green top tubes (e.g. six 10 cc tubes filled approximately to 10 mL) at the time points listed in the Study Flow Chart in Section 6.0. The tubes will be delivered directly to the UCSF Immune Monitoring Core for PBMC isolation then freezing for future analysis in batch at end of study and pending funding. See Appendix 11.6 for correlative specimen procurement and handling instructions.

7.1.4.3 Expansion Cohort Research Biopsies

Expansion Cohort enrollment requires radiographic assessment of measurable disease by RECIST 1.1 with ≥ 1 target lesion not planned for biopsy, as well as tumor accessible to minimally-invasive percutaneous biopsy (by CT, ultrasound, or punch) based upon assessment of qualified radiologist. More invasive methods of biopsy such as surgery, laparoscopy, or endoscopy are not allowed for purposes of research biopsy on this study due to patient risk. Consent for paired research biopsies during Cycle 1 and Cycle 3 is required for enrollment to Expansion Cohort. Two to 4 core needle biopsies (CNB), preferred 18-gauge and 1 cm depth (or equivalent) if safely accessible based upon evaluation by proceduralist, should be obtained at each time point (Section 6.4) with prioritization and handling instructions per Appendix 11.6.3. Biopsy samples will be analyzed for exploratory biomarker endpoints as described in 4.3.6.4

7.1.4.4 Specimen Banking

For patients enrolled at UCSF who consent to optional specimen banking, all left-over blood and/or tumor samples will be banked in the UCSF Hepatobiliary Tissue Bank, CC#124512.

See Appendix 11.6 for correlative specimen procurement and handling instructions.

7.1.5 Other Procedures

7.1.5.1 Re-Induction with GM-CSF

In patients who demonstrate CR, PR, or prolonged stable disease \geq 6 months with evidence of clinical benefit (such as minor response radiographically, decline in CA 19-9, and/or improved symptoms) after the Induction Phase but within 12 months from enrollment, but who subsequently progress on single-agent pembrolizumab between 6-12 months after enrollment (after the primary endpoint of PFS6 has been ascertained for that patient), re-induction with GM-CSF may be administered in case-by-case situations with approval from Study Chair provided patient remains eligible for ongoing treatment on protocol (section 7.1.5.3).

7.1.5.2 Second Course Pembrolizumab

Subjects who stop pembrolizumab with SD or better may be eligible for up to one year of additional pembrolizumab therapy if they progress within 6 months after stopping study treatment, without any evidence of progression prior to discontinuation, with case-by-case approval from Study Chair and Merck. This retreatment is termed the Second Course of this study and is only available if the study remains open to enrollment and the subject meets the following conditions:

- **Either**

- Stopped initial treatment with pembrolizumab after attaining an investigator-determined confirmed CR according to RECIST 1.1, and:
 - Was treated for at least 24 weeks with pembrolizumab before discontinuing therapy.
 - Received at least two treatments with pembrolizumab beyond the date when the initial CR was declared.

OR

- Had CR, PR, or SD with evidence of clinical benefit (such as minor response radiographically, decline in CA 19-9, and/or improved symptoms) and stopped pembrolizumab treatment after 24 months of study therapy due to protocol-defined treatment duration, without any evidence of disease progression or intolerance.

AND

- Experienced an investigator-determined confirmed radiographic disease progression within 6 months after stopping their initial treatment with pembrolizumab.
- Did not receive any other anti-cancer treatment since the last dose of pembrolizumab.

- Meets original entry criteria in Section 5.1 (with exception of exclusion 19 which is not applicable to re-induction or Second Course).

Subjects who restart treatment will be retreated at the same dose and dose interval as when they last received pembrolizumab. Treatment will be administered for up to one additional year.

7.1.5.3 Withdrawal/Discontinuation

When a subject discontinues/withdraws prior to trial completion, all applicable activities scheduled for the final trial visit should be performed at the time of Safety Follow-Up Visit (Section 6). Any adverse events which are present at the time of discontinuation/withdrawal should be followed in accordance with the safety requirements outlined in Section 7.2 - Assessing and Recording Adverse Events. Subjects who a) attain a CR or b) complete 24 months of treatment with pembrolizumab may discontinue treatment with the option of restarting treatment if they meet the criteria specified in Section 7.1.5.2. After discontinuing treatment following assessment of CR, these subjects should return to the clinic for a Safety Follow-Up Visit (described in Section 7.1.5.3.1) and then proceed to the Follow-Up Phase of the study (described in Section 7.1.5.4).

7.1.5.4 Blinding/Unblinding

Not applicable to this study.

7.1.6 Visit Requirements

7.1.6.1 Screening, On-Treatment, and Discontinuation/End of Treatment Visits

Visit requirements for the main study are outlined in Section 6.2 –Main Study Flow Chart. Specific procedure-related details are provided above in Section 7.1 - Trial Procedures.

7.1.6.2 Re-Induction with GM-CSF

Visit requirements for patients eligible for re-induction with GM-CSF are outlined in Section 6.0 – Main Study Flow Chart. Specific procedure-related details are provided above in Section 7.1 - Trial Procedures and 7.1.5.1 – Re-Induction with GM-CSF.

7.1.6.3 Post-Treatment Visits

7.1.6.3.1 Safety Follow-Up Visit

The mandatory Safety Follow-Up Visit should be conducted approximately 30 days after the last dose of trial treatment or before the initiation of a new anti-cancer treatment, whichever comes first. Though the Safety Follow-Up Visit and assessments should be performed at UCSF when possible, safety follow up assessments (including administrative, clinical, laboratory, and efficacy assessments, see Sections 6.1-6.3) may be extracted from clinical data obtained from a subject's local physician's office visit, during a hospitalization, and/or during any other standard medical encounter, if travel to UCSF would confer hardship due to distance and/or due to initiation of new therapy. All AEs that occur prior to the Safety Follow-Up Visit should be recorded. Subjects with

an at least possibly treatment-related AE of Grade > 1 will be followed until the resolution of the AE to Grade 0-1, assessment as chronic or irreversible by investigator, or until the beginning of a new anti-neoplastic therapy, whichever occurs first. SAEs that occur within 90 days of the end of treatment or before initiation of a new anti-cancer treatment should also be followed and recorded.

Subjects who are eligible for Second Course of pembrolizumab (as described in Section 7.1.5.4.1) may have up to two Safety Follow-Up visits, one after the Treatment Period and one after the Second Course.

7.1.6.4 Follow-Up Phase

Subjects who discontinue trial treatment for a reason other than disease progression will move into the Follow-Up Phase and should be assessed every 8 weeks (± 28 days) by radiography to monitor disease status. After 1 year, the imaging time point will occur every 12 weeks (± 28 days) or more often if clinically indicated. After 2 years in Follow-Up Phase, patients will discontinue active follow up and be followed only for survival according to Survival Follow-Up Phase (Section 7.1.6.4.2). Every effort should be made to collect information regarding disease status until the start of new anti-neoplastic therapy, disease progression, death, end of the study or if the subject begins retreatment with Second Course pembrolizumab as detailed in Section 7.1.5.2. Information regarding post-study anti-neoplastic treatment will be collected if new treatment is initiated.

7.1.6.4.1 Second Course Pembrolizumab

Subjects who are eligible to receive retreatment with pembrolizumab according to the criteria in Section 7.1.5.2 will move from the Follow-Up Phase to the Second Course when they experience disease progression. Visit requirements are provided in Section 6.3 – Second Course Pembrolizumab Flow Chart. Specific procedure-related details are provided above in Section 7.1 – Trial Procedures and 6.3 – Second Course Pembrolizumab Flow Chart.

7.1.6.4.2 Survival Follow-Up Phase

Once a subject experiences confirmed disease progression, starts a new anti-cancer therapy, has no evidence of progression after 2 years in Follow-Up Phase (Section 7.1.6.4), or transitions to palliative/end of life care, the subject moves into the Survival Follow-Up Phase. Survival status should be ascertained by clinic visit (if appropriate for patient's medical care, chart review, or by telephone contact approximately every 12 weeks ± 28 days to assess for survival status until death, withdrawal of consent, or the end of the study, whichever occurs first).

7.2 Assessing and Recording Adverse Events

An adverse event is defined as any untoward medical occurrence in a patient or clinical investigation subject administered a pharmaceutical product and which does not necessarily have to have a causal relationship with this treatment. An adverse event can therefore be any unfavorable and unintended sign (including an abnormal laboratory finding, for example), symptom, or disease temporally associated with the use of a medicinal product or protocol-specified procedure, whether or not considered related to the medicinal product or protocol-specified procedure. Any worsening (i.e., any clinically significant adverse change in frequency and/or intensity) of a preexisting

condition that is temporally associated with the use of the investigational product(s), is also an adverse event. Adverse events may occur during the course of the use of the investigational products during the Treatment Period or within the Follow-Up Phase of this study. Progression of the cancer under study is not considered an adverse event unless it is considered to be drug related by the investigator.

The investigational products in this study are pembrolizumab and GM-CSF.

All adverse events will be recorded from the time the consent form is signed through 30 days following cessation of treatment and at each examination on the Adverse Event case report forms/worksheets. The reporting timeframe for adverse events meeting any serious criteria is described in section 7.2.3.

7.2.1 Definition of an Overdose for This Protocol and Reporting of Overdose to the Study Chair and to Merck

For purposes of this trial, an overdose of pembrolizumab will be defined as any dose of 1,000 mg or greater or GM-CSF 1250 µg or greater in a single dose (≥ 5 times the indicated dose). No specific information is available on the treatment of overdose of pembrolizumab. Appropriate supportive treatment should be provided if clinically indicated. In the event of overdose, the subject should be observed closely for signs of toxicity. Appropriate supportive treatment should be provided if clinically indicated.

If an adverse event(s) is associated with (“results from”) the overdose of a Merck product, the adverse event(s) is reported as a serious adverse event, even if no other seriousness criteria are met.

If a dose of Merck’s product meeting the protocol definition of overdose is taken without any associated clinical symptoms or abnormal laboratory results, the overdose is reported as a non-serious ECI, using the terminology “accidental or intentional overdose without adverse effect.”

All reports of overdose with and without an adverse event must be reported within 24 business hours to the Study Chair and within 2 business days to Merck Global Safety, from the time of investigator awareness. See Appendix 11.7.

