5.2.2.1 Dose Modifications for Pembrolizumab

Adverse events (both non-serious and serious) associated with pembrolizumab exposure may represent an immunologic etiology. These adverse events may occur shortly after the first dose or several months after the last dose of treatment. Pembrolizumab must be withheld for drug-related toxicities and severe or life-threatening AEs as per Table 3 below. As toxicity on pembrolizumab has not been shown to be dose related, dose reductions are not thought to ameliorate specific toxicities. See Section 5.6.1 and Events of Clinical Interest Guidance Document for supportive care guidelines, including use of corticosteroids.

Table 3 Dose Modification Guidelines for Pembrolizumab-Related Adverse Events

Toxicity	Hold Treatment For Grade	Timing for Restarting* Treatment	Discontinue Subject
Diarrhea/colitis	2-3	Hold until toxicity resolves to Grade 0-1	If toxicity does not resolve within 12 weeks of last dose or inability to reduce corticosteroid to 10 mg or less of prednisone or equivalent per day within 12 weeks
	4	Permanently discontinue	Permanently discontinue
AST, ALT, or increased bilirubin (despite optimal supportive care including biliary drainage if obstruction is present)	2 ^{1-3²}	Hold until toxicity resolves to Grade 0-1 or baseline grade (if Grade 2 at baseline) ¹	If toxicity does not resolve within 12 weeks of last dose
	3 ²⁻⁴	Permanently discontinue	Permanently discontinue
Type 1 diabetes mellitus (if new onset) or hyperglycemia	T1DM or 3-4	Hold for new onset Type 1 diabetes mellitus or Grade 3-4 hyperglycemia associated with evidence of beta cell failure; resume pembrolizumab when patients are clinically and metabolically stable	If toxicity does not resolve within 12 weeks of last dose or inability to reduce corticosteroid to 10 mg or less of prednisone or equivalent per day within 12 weeks
Hypophysitis	2-3	Hold until toxicity resolves to Grade 0-1	If toxicity does not resolve within 12 weeks of last dose or inability to reduce corticosteroid to 10 mg or less of prednisone or equivalent per day within 12 weeks
	4	Permanently discontinue	Permanently discontinue
Hyperthyroidism	3	Hold until toxicity resolves to Grade 0-1	If toxicity does not resolve within 12 weeks of last dose or inability to reduce corticosteroid to 10 mg or less of prednisone or equivalent per day within 12 weeks
	4	Permanently discontinue	Permanently discontinue

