6.0 STUDY FLOW CHARTS

6.1 Safety Cohort Flow Chart (Safety Population)

Trial Period:	Screening Phase ^b	Treatment Cycles ^a										End of Treatment	Post-Treatment		
		Cycle (C) 1			C2, C3			To be repeated on D1 each cycle beyond 8 cycles					Safety Follow-Up Visit ^b	Follow-Up Visits ^b	Survival Follow-Up
Treatment Cycle/Title:	Main Study Screening	Day (D) 1	D8	D15	D1	D8	D15	C4 D1	C5 D1	C6 D1	C7 D1	C8 D1			
													Approx. 30 days (± 14 days) post last treatment	Every 8 weeks ± 28 days for 1 year post last treatment. then every 12 weeks ± 28 days	Every 12 weeks ± 28 days
Scheduling Window (Days):	-28 to 1	± 3	± 3	± 3	± 3	± 3	± 3	± 3	± 3	± 3	± 3	± 3			
Administrative Procedures															
Informed Consent	X														
Inclusion/Exclusion Criteria	X														
Demographics and Medical History	X														
Prior and Concomitant Medication Review	X	X	X	X	X	X	X	X	X	X	X	X	X		
Pembrolizumab Administration ^a		X			X			X	X	X	X	X			
GM-CSF Administration Days 1-14 ^{a,m}					D1-14 ^m										
GM-CSF Patient Diary/Injection Record ^{c,m} (Appendix 11.2)					X ^m			X ^m							
Post-Study Anticancer Therapy Status													X	X	X
Survival Status													X	X	X
Clinical Procedures/Assessments															
Review Adverse Events	X	X	X	X	X	X	X	X	X	X	X	X	X ^d		
Full Physical Examination	X	X	X	X ^o	X	X	X ^o	X	X	X	X	X	X		
Vital Signs and Weight	X	X	X	X ^o	X	X	X ^o	X	X	X	X	X	X		
ECOG Performance Status (Appendix 11.4)	X	X			X			X	X	X	X	X	X		
Child Pugh Score (Appendix 11.5)	X														

Trial Period:	Screening Phase ^b	Treatment Cycles ^a										End of Treatment	Post-Treatment					
		Cycle (C) 1			C2, C3			To be repeated on D1 each cycle beyond 8 cycles				Safety Follow-Up Visit ^b	Follow-Up Visits ^b	Survival Follow-Up				
Treatment Cycle/Title:	Main Study Screening	Day (D) 1	D8	D15	D1	D8	D15	C4 D1	C5 D1	C6 D1	C7 D1	C8 D1						
													Approx. 30 days (±14 days) post last treatment	Every 8 weeks ±28 days for 1 year post last treatment, then every 12 weeks ±28 days	Every 12 weeks ±28 days			
Laboratory Procedures/Assessments: analysis performed by LOCAL laboratory																		
Pregnancy Test – Urine or Serum β-HCG ^e	X	X			X			X	X	X	X	X						
PT/INR	X	X	X	X	X	X	X	X	X	X	X	X	X					
aPTT	X	X	X	X	X	X	X	X	X	X								
CBC with Differential ⁿ	X	X	X	X	X ⁿ	X ⁿ	X	X	X	X	X	X	X					
Comprehensive Serum Chemistry Panel ^f	X	X	X	X	X	X	X	X	X	X	X	X	X					
Urinalysis ^g	X	Every 8 weeks from C1D1 ± 14 days									X							

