7.1.2 Clinical Procedures/Assessments

7.1.2.1 Adverse Event (AE) Monitoring

The investigator or qualified designee will assess each subject to evaluate for potential new or worsening AEs as specified in the Trial Flow Chart and more frequently if clinically indicated. Adverse experiences will be graded and recorded throughout the study and during the Follow-Up Phase according to NCI CTCAE Version 4.0 (see Appendix 11.3). Toxicities will be characterized in terms regarding seriousness, causality, toxicity grading, and action taken with regard to trial treatment.

All AEs of unknown etiology associated with pembrolizumab exposure should be evaluated to determine if it is possibly an immune-related adverse event (irAE). Please refer to section 7.2 for detailed information regarding the assessment and recording of AEs and irAEs.

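### The protocol gives three different ends for recording adverse events, and two of them can fall before the 9-week window of the Grade ≥3 safety endpoint has closed.

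*Combined protocol and SAP*

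**What the plan says.** Three places set the period for recording adverse events of any kind.

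- Section 7.2: "All adverse events will be recorded from the time the consent form is signed through 30 days following cessation of treatment". The sentence goes on to require recording at each examination. Section 5.8 also gives 30 days.
- Section 7.1.6.3.1: "All AEs that occur prior to the Safety Follow-Up Visit should be recorded". That visit is due "approximately 30 days after the last dose of trial treatment or before the initiation of a new anti-cancer treatment, whichever comes first". The flow chart in Section 6.1 gives its timing as "Approx. 30 days (± 14 days) post last treatment", and 6.2 to 6.4 use the same window.
- Section 7.1.2.1: "Adverse experiences will be graded and recorded throughout the study and during the Follow-Up Phase according to NCI CTCAE Version 4.0". For patients who stop without progression, that phase can run for two years (Section 7.1.6.4: "After 2 years in Follow-Up Phase, patients will discontinue active follow up").

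In the flow charts, the adverse-event review row has no mark after the Safety Follow-Up Visit.

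Serious events have their own rule in Section 7.2.3.1: 90 days or new anti-cancer therapy, whichever is earlier, with related serious events reportable at any time after that.

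The endpoint concerned is in Section 3.2: a related Grade ≥3 rate of at most 50% over the first three cycles. Sections 8.4.4 and 8.5.1 give that period as 9 weeks. Section 8.5.1 limits the safety population to patients who have had both drugs at least once and could have completed the 9 weeks.

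**The concern.** An incidence over a fixed window is interpretable only if every patient in the denominator is observed for that window, or if the analysis says how shorter observation is handled. Here recording runs from the last dose, while the endpoint runs from the first. A patient who stops early can leave adverse-event recording before the window closes and still count as having had no event. Section 8.5.1 replaces some patients who are not evaluable before 9 weeks, but its examples are ineligibility, withdrawn consent and biliary complications unrelated to tumour or treatment. Stopping for toxicity or progression is not among them, so those patients stay in the denominator.

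The conflict between sections adds a second problem. A coordinator following 7.1.2.1, one following 7.2 and one closing the log at the Safety Follow-Up Visit would each record a different period. At stake is some downward bias in the related Grade ≥3 rate, and uneven ascertainment between patients.

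**Working it through.** **Inputs.** Cycle length is 21 days (flow-chart footnotes). The endpoint window is three cycles (Sections 3.2, 8.5.1). Recording ends 30 days after treatment (7.2) or at a visit 30 ± 14 days after it (6.1). GM-CSF is given on Days 1–14 of Cycles 2 and 3 in the Safety and Expansion Cohorts, and of Cycles 1 and 2 in the Efficacy Cohort (Table 2). Day 1 is the first dose, cessation of treatment is taken as the last dose of either drug, and the ±3-day cycle windows are ignored.

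**The plan's own figure.** 3 × 21 = 63 days = 9 weeks, as Sections 8.4.4 and 8.5.1 state.

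**Closing day.** With last dose on Day L and a recording interval of w days, recording closes on Day L + w and the shortfall is 63 − (L + w). The earliest scheduled visit has w = 30 − 14 = 16, and the latest has w = 30 + 14 = 44.

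Recording closes before Day 63 when L ≤ 62 − w:
- w = 30: L ≤ 32
- w = 16: L ≤ 46
- w = 44: L ≤ 18

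**Who can be affected.** Safety and Expansion patients first receive GM-CSF on Cycle 2 Day 1, so L = 22 is their earliest last dose that still places them in the safety population. Efficacy Cohort patients receive both drugs on Day 1, so L = 1 is possible there.

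| Last dose | Cohorts in the safety population | 30-day rule: closes (short by) | Earliest scheduled visit: closes (short by) |
|---|---|---|---|
| C1D1, Day 1 | Efficacy only | Day 31 (32) | Day 17 (46) |
| C1D14, Day 14 | Efficacy only | Day 44 (19) | Day 30 (33) |
| C2D1, Day 22 | All | Day 52 (11) | Day 38 (25) |
| C2D14, Day 35 | All | Day 65 (covered) | Day 51 (12) |
| C3D1, Day 43 | All | Day 73 (covered) | Day 59 (4) |

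As shares of the window: 11/63 = 17%, 25/63 = 40%, 32/63 = 51%.

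If new anti-cancer therapy begins first, the visit moves forward with no minimum interval, so the visit-based shortfall can exceed the last column.

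**Which events can be missed.** For serious events the earliest close is 1 + 90 = Day 91, beyond Day 63 unless new therapy intervenes. Related events above Grade 1 that are already recorded are followed to resolution, to assessment as chronic or irreversible, or to new therapy (7.1.6.3.1). What remains is a new, non-serious event after recording closes. A non-serious related Grade 3 event of that kind would count toward the 50% criterion.

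**The case against.** The strongest reply is that these passages set minimum duties and do not tell anyone to stop. Section 7.1.6.3.1 requires events before the visit to be recorded; it does not say that a Day 16 visit cancels the 30-day duty in 7.2. Section 7.1.2.1 refers the reader to 7.2 for detail. Appendix 11.1 sends all Grade 3–5 events to the trial database without an end date. On this reading the rule is 30 days for all events and 90 days for serious ones. That is a reasonable reading, and it would remove the visit-based figures. It does not remove the 11-day gap after a last dose on Day 22, and the text does not say that this reading governs.

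A second reply is that most permanent-discontinuation triggers in Tables 3 and 4 are Grade 3–4. A patient who stops for one is probably already counted, and a later event cannot raise a per-patient rate. This stands, and it weakens any claim of large bias. The gap then matters for patients who stop early for another reason, such as progression or lower-grade intolerance.

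Four stronger readings do not hold.

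- A reader might infer that half the window is lost for a Safety or Expansion patient who stops after the first pembrolizumab dose. That patient has had no GM-CSF and is outside the safety population.
- The 30-day and 90-day limits might look contradictory. They are a deliberate tier for different kinds of event.
- Section 5.2.2.1 says of pembrolizumab-associated events: "These adverse events may occur shortly after the first dose or several months after the last dose of treatment". That does not show that a first-three-cycles endpoint needs recording for months. Following non-serious immune events to Day 90 is a preference.
- It might seem that non-serious Grade ≥3 events after Day 30 are never collected. Appendix 11.1 and the at-each-examination wording in 7.2 make that too absolute.

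**Conclusion.** The point holds as an inconsistency with a limited consequence. Sections 7.2, 7.1.6.3.1 and 7.1.2.1 do not give one end of recording, and under the first two a patient who stops early can leave recording before Day 63 while remaining in the denominator. For the Safety and Expansion Cohorts the shortfall is at most 11 days under the 30-day rule, or 25 days if the earliest scheduled visit ends recording. The 32-day figure under the 30-day rule belongs to the Efficacy Cohort alone, whose enrolment is complete. Patients dosed on Cycle 3 Day 1 and recorded for the full 30 days are covered.

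The documents give no rate of early stopping or of late non-serious Grade ≥3 events, so the effect on the percentage cannot be computed. It is probably small, and it is nil for a patient who already has a counted event. The reported interim rate of 11% in nine patients fits one patient (1/9). If the criterion is per patient, exceeding 50% would have taken five (5/9 = 56%), so four more patients with an event. Nothing in the documents suggests that the interim Grade ≥3 finding was wrong. The day counts assume the nominal schedule and the last dose of either drug as the reference date.

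**What to change.** Reconcile Sections 6.1–6.4, 7.1.2.1, 7.1.6.3.1 and 7.2 to a single end-of-recording rule. In every safety-population patient, record all adverse events to the later of 30 days after the last dose or Day 63, whatever the date of the Safety Follow-Up Visit. State whether events after new anti-cancer therapy count toward the three-cycle rate. Keep the 90-day tier for serious events; extending non-serious immune events to Day 90 is optional.

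For the completed cohorts, report how many safety-population patients had recording that ended before Day 63. If there are none, the question is closed for them.

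The cost is protocol wording and a little extra data entry for a few early stoppers. The flow charts schedule no adverse-event review after the Safety Follow-Up Visit, so these patients need one added contact or chart review near Day 63. The 90-day serious-event rule already calls for information over that period unless new therapy has started. Treatment does not change.
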